The parents and adolescents will be given the option to download an electronic copy of the signed online informed consent form for their own records or a copy of the one-page parent permission consent form that they reviewed.

Parents and adolescents may use their computers to sign the e-consent.

If research staff are to work with parents, adolescents, and ASP staff inside the ASP facility, research staff will follow COVID-19 guidelines put in place by the ASP. Research staff will wear masks, use hand sanitizer, and will distance themselves from others by at least 6 feet. If someone at the facility were to test positive for COVID-19, all who were in contact with the positive case will be required to quarantine for 2 weeks.

[figure not shown]
It is expected that 1000 adolescents and their parent/legal guardian will be interested and eligible. Parental permission and child assent forms will be presented online, and in detail by a study staff or the PI.

Both program implementers and ASP staff members will receive adult consents to participate in focus group discussions and interviews.

- **Baseline assessment at Day 1:** In a classroom setting, participating adolescents will be invited to complete the baseline 20-minute psychosocial survey (time 1) and the baseline 20-minute social network survey (time 1).
- **Randomization at Day 1:** Immediately after baseline assessment at Day 1, the participating clubs will be randomly assigned to either ASPIRE or GSA-ASPIRE-Network. Details on each intervention are described in the following sections. After-school programs (ASPs) will be randomized in a single-blinded format to 1 of 2 conditions: the ASPIRE program or the GSA-ASPIRE-Network program. We will use a covariate-constrained approach in randomizing ASPs to minimize between-group differences in club characteristics (e.g., adolescent volume in a cluster, proportion of adolescents with intent to use tobacco or users, age, gender).

- **Orientation at Day 1:** Also, after baseline assessment at Day 1, participants will receive a session of orientation, allowing them to learn how to take part in the program (ASPIRE or GSA-ASPIRE-Network), depending on their assigned condition. The orientation will be in the form of a presentation and some attempts at engaging in the program for the first time.

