- **Intervention details:** The first session of the assigned intervention (ASPIRE or GSA-ASPIRE-Network) will occur three to five days after orientation (depending on the ASP's availabilities).
  - › In the ASPIRE condition (other treatment), participants will engage in five 70-minute sessions of ASPIRE spread over a period of 5 weeks (1 session per week). During each session, participants will alternate between 10 minutes of ASPIRE use and 5-minute breaks.
  - › In the GSA-ASPIRE-Network condition (intervention), on the other hand, participants from each club (expected to be between 24 and 50 participants) will be purposely seated in groups, with 3 to 6 adolescents per group. Participants' group allocation will be determined based on findings from social network analysis (details below). Each group will engage in five 70-minute sessions of ASPIRE spread over 5 weeks (1 session per week). During each session, participants will either receive ASPIRE, or the GSAs, or both. Along with the game board, GSA content will be presented to participants via the "Kahoot! 360 Pro" platform. Study data will not be captured nor stored on Kahoot. Participants will not complete any assessment question of identifiable questions via "Kahoot!". They will engage in the program as a team. After each session, with a timeline of a week, participants will have the opportunity to engage in off-session activities at their own pace. These activities will allow participants to practice what they learn during the sessions. To receive credit for completing the activities, participants will be asked to keep track of their progress in these activities and present evidence of completing the activities. To this end and depending on the activities, they may record themselves completing the activity via photo or video and submitting the recording to the research team via the secure system REDCap. Recording and submitting the photos or videos will not be required to participate in the research project, and alternative methods of presenting evidence of activity completion will be provided. If participants choose to submit videos or photos for their activities, they will be asked to capture these videos and photos without having a non-participant in the background. If a non-participant is visible in the background, the recording will be censored to remove the non-participant.

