  - › Adolescents who decline to be part of the study will engage in the usual ASP activities provided by the ASP staff. These activities are comparable to the "control" (non-network) condition, but without the surveying.
- **Additional assessment points:** In addition to baseline (time 1: Assessment 1), all participants will complete psychosocial surveys and social network surveys after 3 sessions (i.e., mid-intervention; time 2: Assessment 2), following the last session (i.e., post-intervention; time 3: Assessment 3), and 2 to 3 weeks post-intervention (i.e., follow-up; time 4, or assessment 4). After time 4, we will conduct one-on-one interviews with 60 adolescents randomly selected from ASPIRE (n=30) and GSA-ASPIRE-Network (n=30). We will also conduct exit interviews with 2 ASP staff members per ASP and all program implementers. Exit interviews and the intervention sessions will be audio-recorded, in order to capture user's experience. Survey assessments 5 through 8 will also be completed as delineated in the above study design for Study 2. Figure 1 presents the study flow diagram.

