**Figure 1. Study Flow Diagram**

**Note:** Approximate days: Assessment 1 and orientation at day 1 (time 1, baseline), session 1 at 3-5 days after assessment 1, session 2 and assessment 2 (time 2; mid-intervention) at day 12, session 3 at day 19, session 4 and assessment 3 (time 3, post-intervention) at day 26, and assessment 4 (time 4 or assessment 4, follow up) at day 56, assessment 5 at 1 month after assessment 4, Assessment 6 immediately after GSA-Network, assessment 7 at 2-3 weeks later, and assessment 8 at 1 month after A7.

- Instruments for Study 2.** Several variables will be measured through psychosocial (Measures in Appendix 3), and social network surveys (Appendix 4), using previously validated measures delineated below. In a private classroom setting, a study staff or the PI will conduct and collect the surveys and audio recordings.

- **Psychosocial survey:** At all 4 time points, the psychosocial survey will measure tobacco use status and intention to use tobacco. At time 1, this survey will include psychosocial determinants of smoking and factors that may affect an online experience, social influence, social activity engagement, and game play. At time 3 only, the psychosocial survey will include measures to check for any expected differences and similarities between groups (i.e., manipulation check): Attitude toward the intervention, perceived medium interactivity, perceived social interactivity, and perceived entertainment value. To capture adolescents' tendency to positively influence others, the survey will measure interpersonal communication, ability to persuade others, and diffuse health information to others.

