Susceptibility to use tobacco is a clinical and epidemiological screening questionnaire of 3 items that has been shown to be the most potent predictor of actual tobacco initiation among adolescents. The continuous version of this scale is termed “intention to use tobacco”. Sample size and power have been calculated based on the hypothesized difference between groups that render participants in the GSA-ASPIRE-Network group non-susceptible to use tobacco, based on the “intention to use tobacco” scale and previous research.

Sample size calculation is done for H1 and satisfies H2. These power estimates are conservative. We will have more power using mixed-effect models. Sample size was calculated based on 2 clusters per arm, however, we will have more power with the proposed 8 clusters (4 clusters per arm). Considering that about 33% of adolescents generally intent to use tobacco, the required sample size is 300 participants. Considering 40% retention and 50 potential non-eligible, we will recruit 800 participants. In addition to this sample size, we will work to reach a representative Florida sample of adolescents. For the interviews, thematic saturation with adolescents is expected by 60 interviews (20% of the final 300 participants).

- **Quantitative data analysis for Study 2.** To test H1, a linear mixed-effect model (LMM) will be conducted to compare the conditions with respect to intention to use tobacco (continuous outcome variable), in a 2 (condition)  $\times$  4 (time) design. Using a second LMM, the 2 conditions will be compared over time with respect to positive social influence. In both models, intervention effects on outcome trajectories over time will be measured with the condition  $\times$  time interaction term. To test H2, a third LMM will be conducted with positive social influence as a mediator. Each individual will be modeled as a random effect nested within the club, club membership will be modeled as a random effect nested within treatment condition, and treatment will be modeled as a fixed effect. If manipulation checks indicate problems, particularly differences or similarities between arms that are not supposed to occur, we will control for such differences or similarities within our models.

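### The H1 models may be adjusted for manipulation checks measured after randomisation, and no unadjusted H1 model is kept primary

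*Combined protocol and SAP*

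**What the plan says.** All references are to Section 7 of the combined protocol and SAP unless stated.

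- **H1 models (Quantitative data analysis for Study 2).** Intention to use tobacco and positive social influence are each analysed with a linear mixed model over four times. "In both models, intervention effects on outcome trajectories over time will be measured with the condition" × time interaction. No covariates are listed.
- **Adjustment rule (same paragraph).** "If manipulation checks indicate problems, particularly differences or similarities between arms that are not supposed to occur", then "we will control for such differences or similarities within our models".
- **The checks (Instruments for Study 2, Psychosocial survey).** "At time 3 only, the psychosocial survey will include measures to check for any expected differences and similarities between groups (i.e., manipulation check"). Four measures follow: attitude to the intervention, interactivity of the medium, social interactivity, and entertainment value.
- **Timing of time 3.** Additional assessment points places it "following the last session (i.e., post-intervention; time 3: Assessment 3"). The Figure 1 note has "session 4 and assessment 3 (time 3, post-intervention) at day 26".
- **Timing of randomisation (Randomization at Day 1).** "Immediately after baseline assessment at Day 1, the participating clubs will be randomly assigned to either ASPIRE or GSA-ASPIRE-Network". Section 8 puts it two days after baseline.
- **What differs between arms (Intervention details).** In the GSA-ASPIRE-Network arm, "They will engage in the program as a team".

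**The concern.** A covariate measured before randomisation cannot be affected by the assigned arm. These checks can be, because they ask participants how they experienced the programme they were given. If the H1 comparison is conditioned on such a variable, it need not estimate the effect of adding social influence strategies to ASPIRE. Part of a real effect can be removed, or an effect can appear where there is none.

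Two features of the rule add to this. The text does not say which of the four checks should differ between arms and which should be alike, nor what counts as a problem, so the choice among them is made after the data are seen. The text also gives no order of precedence. The most natural reading is that, once the rule is triggered, the adjusted model supplies the reported H1 result.

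**Working it through.** The plan gives no figure on this point to reproduce. The check is of timing, then of the form of adjustment, then of size under stated assumptions.

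**1. Timing.** Randomisation is on Day 1 or two days after baseline. Time 3 is with session 4 or after the last session. On every combination the checks come after randomisation.

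**2. Check as a main effect.** A person-constant covariate adds the same amount at each of a participant's four times, so it cancels from change over time. This was tried in 100 simulated null trials of the mixed model (8 clubs × 94 = 752 participants, club and individual random intercepts). With complete data, adjusted minus unadjusted condition × time was 0 (largest 1.4e-17).

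Dropout was then assumed at 80/60/40% retained at times 2/3/4; only the 40% is in the plan. Participants without time 3 were left out of the adjusted model, so 450 of 752 contributed. The mean difference was 0.003 SD and the largest in one trial was 0.083 SD.

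**3. Check entered with time.** Let *a* be the arm difference on the check in SD, and *r* the within-club correlation of check and outcome change. Then:

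shift ≈ a × r × SD(change) × √[(1 − ICC of change)/(1 − check ICC)]

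The last factor is √(0.7/1) = 0.84 for ICCs of 0.3 and 0, and √(0.95/0.7) = 1.17 for 0.05 and 0.3. The figures below take it as 1. In the mixed-model trials, with a = 0.5 and loadings of 0.35 on check and outcome, the expected shift was 0.5 × 0.35 × 0.35 = 0.061 and the observed shift was −0.063.

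**4. On the plan's scales.** Planned differences and SDs are from Sample Size Considerations for Study 2. *a* and *r* are assumed, and the SD of change is assumed equal to the plan's SD.

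| Outcome | Planned difference | Shift at a=0.3, r=0.2 | Shift at a=0.8, r=0.5 |
|---|---|---|---|
| Intention (SD 0.5) | 1.3 − 0.17 = 1.13 | 0.3×0.2×0.5 = 0.03 (2.7%) | 0.8×0.5×0.5 = 0.20 (17.7%) |
| Positive social influence (SD 0.8) | 2.43 − 1.0 = 1.43 | 0.3×0.2×0.8 = 0.048 (3.4%) | 0.8×0.5×0.8 = 0.32 (22.4%) |

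**5. False-positive rate.** Null trials were simulated, 10,000 per cell, with the plan's 8 clubs and 38 participants per club (8 × 38 = 304, close to its 300 completers). The adjustment used the within-club slope, followed by a t-test on club means (6 df). Cells show % rejection for check ICC 0 / 0.3.

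| a, r | Always adjusted, ICC of change 0.3 | Adjusted only if check differs at p<0.05 (assumed trigger), ICC of change 0.3 | Always adjusted, ICC of change 0.05 |
|---|---|---|---|
| 0.3, 0.2 | 5.0 / 5.3 | 5.0 / 5.1 | 5.8 / 5.9 |
| 0.5, 0.35 | 6.3 / 6.1 | 6.3 / 5.7 | 12.0 / 10.8 |
| 0.8, 0.5 | 11.3 / 11.7 | 11.3 / 10.0 | 41.9 / 27.6 |

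Unadjusted rejection was 4.7% to 5.2%. An unexpected similarity (a = 0, r = 0.5, ICC of change 0.3) gave 5.1 / 5.1%. Similarity therefore causes essentially no bias, but a covariate cannot repair it either.

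**The case against.** The strongest reply is that harm needs several things at once: the rule is triggered, the check enters with time, the arm moves the check, the check is linked to outcome change, and the true effect is small. Controlling for a variable in a mixed model is often read as adding a main effect, and in that form the average bias is practically nil. This is correct and limits the severity. It does not settle the matter, because the plan does not restrict itself to that form.

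Second, teamwork raising perceived social interactivity is probably an expected difference, and would then not trigger the rule. That is fair, but the section does not list expected differences, and its wording makes unwanted ones only the main example of a problem. The four candidate measures are named in advance, so only the selection among them depends on the data. The appendix with the measures was not available, and any expectations stated there could not be checked.

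Third, the text does not say outright that the adjusted model replaces the unadjusted one. That is so; the replacement is inferred, and the plan is silent on precedence.

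Fourth, every check input is assumed, 0.3 is the plan's ICC for the outcome and not for its change, and the rejection rates come from club means, not the planned mixed model. With check ICC 0.3, a p<0.05 trigger would fire in only about 9%, 18% and 40% of trials in the three rows. All this stands. The rates illustrate the direction and possible size of the problem and do not predict this trial's error rate.

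The rule also covers the H2 mediation model. That raises different questions and is not taken up here.

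**Conclusion.** The concern holds and should be fixed. The conclusion rests on the text: a stated rule allows the randomised H1 comparison to be conditioned on variables measured after, and open to influence by, assignment, with neither the form of adjustment nor the primary model fixed.

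The size is uncertain. It is nil for a main effect with complete data and negligible for weak links between arm, check and outcome. At the strong end of the assumed range the shift reaches roughly a fifth of the planned differences. The much higher rejection rates at an ICC of change of 0.05 depend heavily on the assumed clustering of the check. Differences as large as those planned would still be seen; the exposure is to a smaller or absent effect. Confidence is high on what the plan says and on the direction of the risk, and lower on any particular magnitude.

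**What to change.** Reword the sentence so that it does not apply to the two H1 models, for example:

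> The H1 models contain no manipulation-check covariates. The checks are reported descriptively by arm as evidence on implementation. Any check-adjusted H1 model is exploratory, its form and its handling of missing time-3 data are stated, and it never replaces the primary H1 result.

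Also state, before the data are seen, which of the four checks are expected to differ between arms and which to be similar. No change to H2 is proposed. The cost is a few lines of analysis wording, with no effect on data collection or operations.

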#### • **Justification for number of participants for Study 1 and study 2**

	Study 1	Study 2	Studies Combined
Participants needed to complete study:	63	300	363
Additional participants enrolled but may discontinue:	30	450	480
Additional participants needed to undergo screening:	7	50	57
Total number of participants:	100	800	900

## **8. Data Safety and Monitoring for Study 1 and Study 2:**

[figure not shown]
- **Responsibility:** The PI will be responsible for data monitoring. The PI will hold responsibility to make sure that the Data and Safety Monitoring Plan outlined below will adhere to the protocol outlined by the institutional review board (IRB) of the University of Florida and the National Institute of Health. The Data Safety and Monitoring Plan is written to ensure the safety of the participants and verifying data validity and integrity. In this project, data will be collected via survey instruments and video and audio recording (during focus group sessions, interviews, program sessions, and off-session activities).
- **Storage of consent documents:** Study staff or the PI will securely store consent documents (both assent forms and parental permissions) in an encrypted and password protected hard drive, and physically locked in the department HOB1.
- **Data collection, management, and storage:** Questionnaire data will be obtained and will assess tobacco use status, intention to use tobacco, beliefs regarding tobacco use, psychological and social determinants of tobacco use behavior, psychological outcomes of intervention-use, social connections, and sociodemographic information. All data will be collected specifically for research purposes and will be coded to maintain confidentiality.

All databases will be stored in a centralized location on one of the departmental servers, which is backed up daily to a hard drive, with access limited to specific users at the discretion of the PI. The PI will assure that audits of selected subsets of data are performed once a month and that appropriate safeguards of participant privacy are maintained. Privacy safeguards will include appropriate password protection and physical security for all computer systems and the external hard drive.

**For Study 2**, data collection will be conducted on computers, through an encrypted and secured online system provided by the institution, the University of Florida. In case there is loss of internet connection, the surveys will be completed on paper. First, following consent, eligible adolescents will complete baseline psychosocial and social network surveys (time 1). Two days after baseline, the clubs will be randomly assigned to either ASPIRE or GSA-ASPIRE-Network. All participants will complete psychosocial surveys and social network surveys after 3 sessions (i.e., mid-intervention; time 2), following the last session (i.e., post-intervention; time 3), 2 to 3 weeks to post-intervention (i.e., follow-up; time 4 or assessment 4).

Assessments 5 through 8 will also be completed as delineated in the above study design. The social network survey will include participants' names. Participants will be assured that this information will remain confidential. During the off-session activities, participants may share via a secure system (REDCap), videos and photos of engagement in these activities. Participants will be asked to capture videos and photos without having a non-participant in the background. If a non-participant is visible in the background, the photo will be censored to remove the non-participant. The videos and photos will be coded and deleted immediately upon completion of coding. A link to these videos and photos will remain stored within REDCap and can only be viewed by the research team in a private room.

**For Study 2**, immediately after the collection of each survey or interview, participant names will be matched with code numbers, and the datasets will become de-identified by deleting names. Replacing names with code numbers for the psychosocial and network surveys will occur during the data collection phase of the study (i.e., immediately after the collection of each survey). The link between names and code numbers will be kept in a separate document only available to the PI. However, the links between codes and names will be discarded immediately after all survey documents have been linked to each other, and no longer than 1 year after the study has ended. Code numbers will be used alone for data analysis. Other than for the assignment to subgroups in the network group, we will not directly be making effort to identify responses, and we will use the links only for matching surveys across times. The figure below delineates this process.

For protection and management, all surveys will be stored securely in an encrypted and password-protected hard drive, and physically locked at the Department HOBI at the University of Florida. Such documents will also be saved in a secured server network in the department HOBI. The research staff and Research Coordinator may have access to the data on an encrypted computer, at the institution only. The data will not leave the institution.

Adolescents' conversations will be audio recorded during focus group discussions (Study 1), interviews (Study 2), and intervention sessions (Study 2). The PI, Research coordinator or other data collector from the research team will ask adolescents to refrain from mentioning anyone's name or any other identifying information during the recordings. The voice recording file is saved under a session number. The voice recorder is then closed and locked in a briefcase right after a session of data collection. The briefcase is taken back to the office and locked at the department HOBI. The voice recording file is reviewed to ensure no mention of identifying information from participants or moderators. Audio recording files will not be in the University of Florida server network to protect the confidentiality of participants. However, they will be kept in an encrypted external hard drive that will stay locked at the Department HOBI at the University of Florida. In case a participant mentions identifying information, an audio software program will be used to erase the segment that mentions identifying information.

**For Study 1**, as we collect surveys and group discussions, participant names will be turned to code numbers in our datasets. Datasets will hence become de-identified. Using code numbers, answers to the focus group discussion will be linked to answers in the questionnaire. The link between names and code numbers will be kept in a separate document only available to the PI. The links between codes and names will be discarded immediately after survey documents have been linked to each other, and no longer than 1 year after the study has ended.

**For Study 1 and Study 2,** Contact information and demographic information will be collected from participants after parents have signed the eConsent or paper consent. Contact information and demographic information will be collected via REDCap survey or via paper form. The contact information of a participant's legal guardian will also be collected. The purpose of obtaining the legal guardian's contact information is to compensate them.

Survey data collection will be conducted online, and survey data will be directly stored online. In case survey data collection must be conducted on paper due to lack of internet, safeguard procedures will be put in place to keep the data safely stored: While names may be initially used during survey taking, they are immediately replaced with code numbers during survey data collection and participants are urged not to provide identifying information. Surveys are collected, closed, and put in folders. Folders are put in a locked briefcase. The briefcase is taken back to the office and locked at the department HOBI. Survey data is manually revised by the PI to report the presence of any identifying information. The survey data is then entered electronically, saved, and kept in the secured server network and an encrypted external hard drive locked at the HOBI at the University of Florida.

For protection and management, all paper-form survey, consent documents, and audio files will be stored securely in an encrypted and password protected hard drive, and physically locked in the department HOBI. Such documents and files will also be saved in a secured server network for the department HOBI.

- **Data entry methods:** For Study 2, while identifying information will be collected (i.e., names), the PI will ensure that the dataset is de-identified immediately after data collection. No identifying information will be collected other than names and mailing addresses. However, code numbers will be used to replace names. The links between codes and names will be discarded immediately after survey documents have been linked to each other, and no longer than 1 year after the study has ended. Other than for the assignment to subgroups in the network group, we will not directly be making effort to identify responses, and we will use the links only for matching surveys across times. The mailing addresses will be used to mail compensation to participants.

For the interviews, the program sessions, and the focus group discussions, the voice and/or video recording file will be transcribed in a locked room by study staff or by a transcription company. The transcript is saved under the session number and kept in the secured server network of the department HOBI. All transcript data will be monitored, and saved under the code number of the participant.

Transcripts will then be thematically analyzed. Such a procedure will be conducted by the research staff and the PI in a private office at the department HOBI. During analysis, only the research team will have access to the data (surveys, transcripts, and audio files).

